3.3.2 Exclusion Criteria

1. Target Disease Exceptions

- a) Location of the NHL in the central nervous system (CNS)

2. Medical History and Concurrent Diseases

- a) Subjects with history of progressive multifocal leukoencephalopathy (PML)
- b) Any positive test for hepatitis B virus, including HBs Ag+ or anti-HBc+, or positive test for hepatitis C virus indicating acute or chronic infection (including anti-HCV+ or presence of HCV-RNA)
- c) Positive test for human immunodeficiency virus (HIV)
- d) Pre-existing neuropathy of \geq grade 2
- e) Any active grade 3 or higher (per the National Cancer Institute's Common Terminology Criteria for Adverse Events [NCI CTCAE], version 4.03) viral, bacterial or fungal infection within 2 weeks prior to the first dose of brentuximab vedotin; routine antimicrobial prophylaxis is permitted.
- f) Documented history of cerebral vascular event (stroke or transient ischemic attack), unstable angina, myocardial infarction or cardiac symptoms with New York Heart Association Class III-IV within 6 months prior to the first dose of the study drugs
- g) Subjects with an active, known or suspected autoimmune disease.

NOTE: Subjects with type I diabetes mellitus, hypothyroidism only requiring hormone replacement, skin disorders (such as vitiligo, psoriasis, or alopecia) not requiring systemic treatment, or conditions not expected to recur in the absence of an external trigger are permitted to enroll.

- h) Subjects with a condition requiring systemic treatment with either corticosteroids (> 10 mg daily prednisone equivalent) or other immunosuppressive medications within 14 days of first dose

NOTE: Inhaled or topical steroids, and adrenal replacement steroid doses > 10 mg daily prednisone equivalent, are permitted in the absence of active autoimmune disease.

- i) Known history of pancreatitis
- j) Other serious underlying medical condition that, in the opinion of the investigator, would impair the ability to receive or tolerate the planned treatment and follow-up
- k) History of another primary invasive malignancy that has not been in remission and is requiring therapy in the last 3 years

3. Prohibited Treatments and/or Therapies

- a) Prior exposure to brentuximab vedotin
- b) Prior exposure to anti-PD1, anti-PDL1, anti-PD-L2, anti-CD137 or anti-CTLA-4 antibody, or any other antibody or drug specifically targeting T-cell co-stimulation or checkpoint pathways
- c) Concurrent enrollment in another therapeutic investigational clinical study

- d) History of hypersensitivity reactions to monoclonal antibody therapy
- e) Prior exposure to anti-CD30 directed treatment
- f) Nitrosoureas within 6 weeks of first dose
- g) Chemotherapy within 4 weeks of first dose
- h) Therapeutic antibodies within 4 weeks of first dose
- i) Radio- or toxin-immunoconjugates within 10 weeks of first dose
- j) Radiation therapy within 3 weeks of first dose, or chest radiation \leq 12 weeks prior to first dose
- k) Investigational agents within 3 weeks of first dose
- l) Carmustine (BCNU) > 1000 mg received as part of pre-transplant conditioning regimen
- m) Received an allogeneic hematopoietic Stem Cell Transplant
- n) Topical and targeted therapies; such as histone deacetylase inhibitors (HDAC inhibitors), anti-folate antagonist, nucleoside analogs or retinoids such as bexarotene, topical nitrogen mustard

4. Allergies and Adverse Drug Reaction

- a) History of allergy or hypersensitivity to study drug components

5. Other Exclusion Criteria

- a) Prisoners or subjects who are involuntarily incarcerated
- b) Subjects who are compulsorily detained for treatment of either a psychiatric or physical (eg, infectious disease) illness
- c) Women who are pregnant or breastfeeding

Eligibility criteria for this study have been carefully considered to ensure the safety of the study subjects and that the results of the study can be used. It is imperative that subjects fully meet all eligibility criteria.

3.3.3 Women of Childbearing Potential

A Women of childbearing potential (WOCBP) is defined as any female who has experienced menarche and who has not undergone surgical sterilization (hysterectomy or bilateral oophorectomy) and is not postmenopausal. Menopause is defined as 12 months of amenorrhea in a woman over age 45 years in the absence of other biological or physiological causes. In addition, females under the age of 55 years must have a serum follicle stimulating hormone, (FSH) level > 40mIU/mL to confirm menopause.

*Females treated with hormone replacement therapy, (HRT) are likely to have artificially suppressed FSH levels and may require a washout period in order to obtain a physiologic FSH level. The duration of the washout period is a function of the type of HRT used. The duration of the washout period below are suggested guidelines and the investigators should use their

judgement in checking serum FSH levels. If the serum FSH level is > 40 mIU/ml at any time during the washout period, the woman can be considered postmenopausal:

- 1 week minimum for vaginal hormonal products (rings, creams, gels)
- 4 week minimum for transdermal products
- 8 week minimum for oral products

Other parenteral products may require washout periods as long as 6 months.

3.4 Concomitant Treatments

3.4.1 Prohibited and/or Restricted Treatments

The following medications are prohibited during the study (unless utilized to treat a drug related adverse event):

- Immunosuppressive agents
- Immunosuppressive doses of systemic corticosteroids (except as stated in Section 3.4.2.1)
- Any concurrent anti-neoplastic therapy (ie, chemotherapy, hormonal therapy, immunotherapy, extensive, non-palliative radiation therapy, or standard or investigational agents)

3.4.2 Other Restrictions and Precautions

Subjects with a condition requiring systemic treatment with either corticosteroids (> 10 mg daily prednisone equivalent) or other immunosuppressive medications within 14 days of first dose are excluded. Inhaled or topical steroids, and adrenal replacement steroid doses > 10 mg daily prednisone equivalent, are permitted in the absence of active autoimmune disease.

It is the local imaging facility's responsibility to determine, based on subject attributes (eg, allergy history, diabetic history and renal status), the appropriate imaging modality and contrast regimen for each subject. Imaging contraindications and contrast risks should be considered in this assessment. Subjects with renal insufficiency should be assessed as to whether or not they should receive contrast and if so, what type and dose of contrast is appropriate. Specific to MRI, subjects with severe renal insufficiency (ie, estimated glomerular filtration rate (eGFR) < 30 mL/min/1.73m²) are at increased risk of nephrogenic systemic fibrosis. MRI contrast should not be given to this subject population. In addition, subjects are excluded from MRI if they have tattoos, metallic implants, pacemakers, etc.

The ultimate decision to perform MRI in an individual subject in this study rests with the site radiologist, the investigator and the standard set by the local Ethics Committee.

3.4.2.1 Permitted Therapy

Subjects are permitted the use of topical, ocular, intra-articular, intranasal, and inhalational corticosteroids (with minimal systemic absorption). Adrenal replacement steroid doses > 10 mg

daily prednisone are permitted. A brief (less than 3 weeks) course of corticosteroids for prophylaxis (eg, contrast dye allergy) or for treatment of non-autoimmune conditions (eg, delayed-type hypersensitivity reaction caused by a contact allergen) is permitted.

Concomitant palliative and supportive care for disease related symptoms (including bisphosphonates and RANK-L inhibitors) is allowed if initiated prior to first dose of study therapy. Palliative radiotherapy must have been completed at least 3 weeks prior to first dose. Palliative radiation therapy is allowed on study, study treatment must be held 2 weeks prior to and 2 weeks post treatment.

The use of platelet and/or red blood cell supportive growth factors or transfusions when applicable is allowed. The use of colony stimulating factors for the treatment of neutropenia per institutional practice is permitted during therapy.

Routine premedication for infusion reactions should not be administered prior to the first dose of study drug(s). However, subjects who experience an infusion-related reaction may receive subsequent treatment with premedication as described in [Section 4.5.6](#).

Subjects who are receiving strong CYP3A4 inhibitors concomitantly with brentuximab vedotin should be closely monitored for adverse reactions.

Routine prophylaxis with vaccines is permitted prior to study entry; it is recommended that vaccines used do not contain live micro-organisms.

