 - Dosing delays to allow for prolonged steroid tapers to manage drug-related adverse events are allowed. Prior to re-initiating treatment in a subject with a dosing delay lasting > 6 weeks, the BMS medical monitor must be consulted. Tumor assessments should continue as per protocol even if dosing is delayed.
 - Dosing delays > 6 weeks that occur for non-drug-related reasons may be allowed if approved by the BMS medical monitor. Prior to re-initiating treatment in a subject with a dosing delay lasting > 6 weeks, the BMS medical monitor must be consulted. Tumor assessments should continue as per protocol even if dosing is delayed.
- Any adverse event, laboratory abnormality, or intercurrent illness which, in the judgment of the Investigator, presents a substantial clinical risk to the subject with continued nivolumab dosing.
- Disease progression as determined by investigator assessment following the guidelines given in [Appendix 2](#) and [Appendix 4](#) with the exception described in [Section 4.5.9](#).
- Subject who initiated the preparative regimen for allogeneic SCT or ASCT any time after the first dose of nivolumab treatment
- Initiation of antineoplastic therapy (ie, chemotherapy, hormonal therapy, immunotherapy, radiation therapy except for palliative radiation therapy, or standard or investigational agents for treatment of cancer)

Subjects who discontinue nivolumab due to a related AE may continue treatment with brentuximab vedotin monotherapy until disease progression or unacceptable toxicity. The same applies in case subjects discontinue brentuximab vedotin due to related AE and chose to continue on nivolumab monotherapy. During Cohort A, however, if subject meets discontinuation criteria within the DLT evaluation period, both drugs must be discontinued.

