8.3 Endpoints

8.3.1 Primary Endpoint(s)

The primary safety endpoints include incidence of deaths, adverse events, serious adverse events, adverse events leading to discontinuation, adverse events leading to dose delay, drug-related adverse events and specific laboratory abnormalities (worst grade). Toxicities will be graded using the National Cancer Institute (NCI) Common Terminology Criteria for Adverse Events (CTCAE) version 4.03.

The primary efficacy endpoint is ORR. It is defined as the number of subjects with a best overall response (BOR) of confirmed CR or PR divided by the number of treated subjects. The BOR is defined as the best response designation recorded between the date of first dose and the date of initial objectively documented progression or the date of subsequent therapy, whichever occurs first. Allogeneic SCT and ASCT will be considered as subsequent therapy. In subjects with relapsed refractory DLBCL, relapsed refractory PTCL, relapsed refractory PMBL and relapsed refractory MGZL the response (CR, PR, PD, and progression) will be assessed according to Lugano Classification 2014. For subjects with relapsed refractory CTCL, response will be assessed according to consensus Global Response Score as per the consensus statement of the International Society for Cutaneous Lymphoma. A CR must have been confirmed by scans, including a negative Positron Emission Tomography (PET) to be considered for CR in subjects with PTCL, DLBCL, PMBL and MZGL. In subjects with PTCL, if the bone marrow was compromised at baseline, a bone marrow must also be negative at the time of CR. In CTCL CT scans (chest, neck, abdomen and pelvis), blood flow for SS cells and m SWAT skin scoring along with medical photography will be performed at baseline and at the end of the treatment for response evaluation. The investigator will perform tests that will allow evaluation of response to therapy according to corresponding disease criteria in [Appendix 2](#) and [Appendix 4](#). The analysis of the primary endpoint will occur approximately 8 months after the last enrolled subject's first dose of study therapy. Depending on the enrollment for each disease cohort, the analysis may be done at different times for each cohort, or at the same time for the three cohorts.

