Abbreviations: CR, complete response; NI, noninvolved; PR, partial response; PD, progressive disease; SD, stable disease.
*It is recommended that not only the proportion of patients who achieve a response or an unfavorable outcome be calculated but a life table account for the length of the interval during which each patient is under observation also be generated.

Response Evaluation in CTCL:

Response in CTCL will be evaluated based on the involvement of different sites (lymph nodes, viscera, skin and blood) using the TNMB staging (as clinically indicated) and will be incorporated in the Global Response Score. The m SWAT will be used for skin scoring.

All responses to be designated as CR or PR, should be documented for at least 4 weeks in duration. No CR can be ascribed to a study drug while a patient remains on concomitant therapy (such as topical steroids) with known efficacy in MF/SS.

In certain cases to document CR a biopsy may be required if there are limitations on Spiral CT scan or MRI examination for lymph node or viscera evaluation and if it is deemed necessary.

Blood evaluation for Sezary syndrome: The absolute number of CD4+ CD26- determined on flow cytometry will be used to assess blood involvement. A normal value for CD+ CD26- or CD4+CD7- cells by flow cytometry is lower than 15%.

Response in skin:

m SWAT for skin scoring/evaluation, to track skin tumor burden.

CR: 100% clearance of skin lesions.

PR: 50%-99% clearance of skin disease from baseline without new tumors (T3) in patients with T1, T2 or T4 only skin disease. ($\geq 50\%$ reduction in the mSWAT score compared with baseline).

Stable disease: $< 25\%$ increase to $< 50\%$ clearance in skin disease from baseline without new tumors (T3) in patients with T1, T2, or T4 only skin disease. (Less than 50% reduction to less than 25% increase in the mSWAT score compared with baseline).

Progressive disease: $> 25\%$ increase in skin disease from baseline or new tumors (T3) in patients with T1, T2 or T4 only skin disease or Loss of response: in those with complete or partial response, increase of skin score of greater than the sum of nadir plus 50% baseline score. Relapse is any disease recurrence in those with complete response. ($\geq 25\%$ increase in the mSWAT score from baseline).

Response in the lymph nodes will be assessed using a Spiral CT Scan or MRI.

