4 ENDPOINTS

4.1 **Primary Endpoints**

The primary safety endpoints include DLT, incidence of deaths, adverse events, serious adverse events, adverse events leading to discontinuation, adverse events leading to dose delay, drug-related adverse events and specific laboratory abnormalities (worst grade). Toxicities will be graded using the National Cancer Institute (NCI) Common Terminology Criteria for Adverse Events (CTCAE) version 4.03.

The primary efficacy endpoint is ORR. It is defined as the number of subjects with a best overall response (BOR) of CR or PR divided by the number of treated subjects. The BOR is defined as the best response designation recorded between the date of first dose and the date of initial objectively documented progression or the date of subsequent therapy, whichever occurs first. Allogeneic SCT and ASCT will be considered as subsequent therapy. In subjects with relapsed refractory DLBCL, relapsed refractory PMBL, relapsed refractory MGZL and relapsed refractory PTCL the response (CR, PR, SD and progression) will be assessed according to Lugano Classification 2014. A CR must have been confirmed by scans, including a negative Positron Emission Tomography (PET) to be considered for CR in subjects with PTCL, PMBL, MGZL and DLBCL. For subjects with relapsed refractory CTCL, response will be assessed according to consensus Global Response Score as per the consensus statement of the International Society for Cutaneous Lymphoma.

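### Permitted local treatment can enter the single-arm ORR: no rule closes BOR at on-study palliative radiotherapy, and the CTCL attribution rule covers CR but not PR

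*Protocol*

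**What the plan says.** **Radiotherapy.** Protocol 3.4.2.1 (Permitted Therapy) states: "Palliative radiation therapy is allowed on study, study treatment must be held 2 weeks prior to and 2 weeks post treatment". Two other sections leave room for it. The prohibited list in 3.4.1 is limited to "extensive, non-palliative radiation therapy, or standard or investigational agents" and similar anticancer treatment. The discontinuation trigger in 4.5.5 covers "radiation therapy except for palliative radiation therapy, or standard or investigational agents for treatment of cancer". SAP 7.2.2 repeats the non-palliative wording, so palliative radiotherapy is not a relevant deviation either.

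**Topical steroids.** Section 3.4.2.1 also states: "Subjects are permitted the use of topical, ocular, intra-articular, intranasal, and inhalational corticosteroids", with minimal systemic absorption as the only qualifier. CTCL skin disease is not mentioned.

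**BOR window.** Protocol 8.3.1 and SAP 4.1 run BOR from first dose to "the date of initial objectively documented progression or the date of subsequent therapy, whichever occurs first". The only expansion of the last term is: "Allogeneic SCT and ASCT will be considered as subsequent therapy".

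**CTCL attribution.** Appendix 4 (Response Evaluation in CTCL) states: "No CR can be ascribed to a study drug while a patient remains on concomitant therapy (such as topical steroids" and the like) known to be effective in MF/SS. The same paragraph asks that both CR and PR be documented for at least 4 weeks, but it attaches no attribution condition to PR.

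**Lesion rules.** Neither Protocol 5.4 nor the Lugano criteria in Appendix 2 excludes or flags an irradiated lesion.

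**The concern.** ORR is meant to measure the combination, and with no control arm nothing else removes the effect of treatment given alongside it. If radiotherapy to a disease site leaves BOR open, a later scan showing that site cleared or shrunken is scored as the criteria read. In CTCL the plan itself recognises the confounder, since Appendix 4 names topical steroids, yet the rule protects only the CR rate. ORR counts PR and CR equally, so a subject denied CR can still be a responder. At stake is whether a cohort's lower confidence limit clears its null because of the study drugs or because of local treatment.

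**Working it through.** **1. Reproduce the plan's figures.** Inputs are from Protocol 8.1 and SAP 5.1 and 7.5.1: two-sided 80% Clopper-Pearson interval, one-sided alpha 10%. The lower limit for x responders of n is the p that solves P(X ≥ x | n, p) = 0.10. The critical count r is the smallest with P(X ≥ r | n, p0) ≤ 0.10.

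| Cohort | n | Null / target | r | Attained alpha | Power, computed (stated) | Lower limit at r | Lower limit at r−1 |
|---|---|---|---|---|---|---|---|
| B1 | 40 | 40 / 60% | 21 | 7.4% | 87.0% (87%) | 41.2% | 38.8% |
| B2 | 30 | 40 / 60% | 16 | 9.7% | 82.5% (82%) | 40.1% | 37.0% |
| B3 | 20 | 60 / 80% | 16 | 5.1% | 63.0% (62%) | 63.9% | 58.5% |
| B4 | 30 | 30 / 50% | 13 | 8.4% | 81.9% (81%) | 30.8% | 27.7% |
| B5 | 10 | 10 / 30% | 3 | 7.0% | 61.7% (61%) | 11.6% | 5.5% |

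The stated intervals reproduce exactly and the powers agree to within about one point. In every cohort the conclusion turns on one response at the boundary. The planned B3 target, 16/20, is itself the boundary. SAP 7.1 pools Cohort A with Cohort B by subtype, so the analysed n may exceed these values and the boundaries would then shift.

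**2. Can the sequence occur under the written rules?** Scans fall at weeks 6 and 12 and then every 9 weeks, regardless of dosing (5.4.1). Section 4.5 allows up to 6 weeks (42 days) from the previous dose. The holds in 3.4.2.1 use 14 + 14 = 28 days, leaving 42 − 28 = 14 days for the radiotherapy course. A subject can therefore be irradiated, stay on study and be scanned afterwards with no progression recorded.

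**3. Can a CTCL subject reach PR this way?** Skin PR is 50–99% clearance. In the mSWAT, tumors carry weight 4, so clearing them lowers the score disproportionately. In the Global Response Score table, skin PR with no other compartment involved and no progression is a global PR. Where Appendix 4 denies CR for other reasons (suspicious skin histology, residual marrow disease), the stated fallback is PR. For concomitant therapy no fallback is stated, and nothing prevents PR.

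**4. Sensitivity range (assumption, not in the documents).** Let m be the share of true non-responders scored as responders because of local treatment, with the true ORR at the null. Apparent ORR = p0 + (1 − p0)m. Example, B3 at m = 5%: 0.60 + 0.40 × 0.05 = 0.62, and P(X ≥ 16 | 20, 0.62) = 7.3%.

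| m | B1 | B2 | B3 | B4 | B5 |
|---|---|---|---|---|---|
| 0 | 7.4% | 9.7% | 5.1% | 8.4% | 7.0% |
| 2% | 9.9% | 12.3% | 5.9% | 11.4% | 10.4% |
| 5% | 14.6% | 16.9% | 7.3% | 17.1% | 16.7% |
| 10% | 25.2% | 26.6% | 10.1% | 29.4% | 29.2% |
| 20% | 53.9% | 51.6% | 18.3% | 59.9% | 56.2% |

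Entries are the chance of wrongly excluding the null, against a planned 10%. B3 starts well below nominal and reaches it only at about m = 10%.

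**The case against.** **The radiotherapy gap is an ambiguity.** A reader might infer that the plan deliberately keeps BOR open after palliative radiotherapy. The documents do not say so. SAP 7.5.2 lists radiotherapy among the subsequent therapies summarised under follow-up therapy, and SAP Table 4.2-1 censors PFS at new anticancer treatment, so a programmer could reasonably close BOR there. Exemption from a drug-discontinuation trigger is not an analysis cutoff. This stands. But the SAP list is a reporting summary that does not mention on-study palliative radiotherapy, and two programmers could derive different BORs from the same subject.

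**Newly started topical steroids for MF/SS are not plainly permitted.** A reader might infer that they are. Section 3.4.2.1 limits supportive care for disease symptoms to care begun before first dose, 3.4.1 bars concurrent antineoplastic therapy, and exclusion criterion 3(n) names topical therapies. None of these names topical steroids for MF/SS, so permission is ambiguous. Steroids unchanged since before baseline are already reflected in baseline mSWAT.

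**The mechanism is narrow.** CR by Lugano needs every site cleared, and CT-based PR needs at least a 50% fall in the summed product over up to 6 lesions. Treating one site seldom achieves either in multi-site disease. Radiotherapy given for documented progression comes after BOR has closed. CTCL PR is scored over all compartments and must last 4 weeks. All of this limits frequency. The 4-week rule addresses persistence, however, and not cause.

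**The size is not specific to this issue.** One response at the boundary would matter under any misclassification, and in the four cohorts other than CTCL radiotherapy would have to do nearly all the work. This stands.

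**Conclusion.** The point holds as a gap in the endpoint rules. As written, a response first seen after on-study radiotherapy to disease can count in ORR, and so can a CTCL PR scored while other effective skin-directed therapy is in use. The plan neither excludes these responses nor measures their influence.

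The firm part of the size is the one-response boundary: for B3 with N=20, 63.9% against 58.5% around a 60% null. The tempting further claim, that false-success rates are materially inflated, is not supported, because the documents give no frequency for either treatment. The range in step 4 shows sensitivity only, and in B3 a 5% misattribution share still leaves the error below 10%.

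Nor do the documents support barring PR in the primary CTCL analysis, since the protocol adopts the consensus Global Response Score. Censoring DOR and PFS at palliative radiotherapy as the main rule is also doubtful: a need for radiotherapy may signal worsening disease, so the censoring could be informative. The gap should be closed before analysis, but it does not undermine the design.

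**What to change.** (a) In Protocol 8.3.1 and SAP 4.1, state that on-study radiotherapy to a disease site counts as subsequent therapy for BOR, so that only assessments up to its start are used. A response already recorded by then is kept.

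(b) Keep the Global Response Score for the primary CTCL ORR. Add a sensitivity ORR that counts as non-responders any subjects whose first response came after on-study radiotherapy to disease or, in CTCL, while on skin-directed therapy known to be effective in MF/SS that was started or increased after baseline mSWAT. Once (a) is in place, the radiotherapy part is already in the primary result and this analysis differs from it only in CTCL.

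(c) For DOR, duration of CR and PFS, apply censoring at palliative radiotherapy as a sensitivity analysis only.

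(d) Reconcile exclusion criterion 3(n), sections 3.4.1 and 3.4.2.1 and Appendix 4 on topical agents in CTCL. The clinical content is for the sponsor to settle.

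(e) Confirm that the CRF captures site and date of on-study radiotherapy, and start and increase dates of topical therapy. The schedule shows concomitant medication review on treatment and subsequent therapy in follow-up, but no section states that these details are recorded.

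Cost: wording in the protocol and SAP, one extra ORR table, sensitivity runs for the time-to-event endpoints and possibly a CRF field. A few responses may be lost, including some truly due to the combination. What subjects may receive does not change.
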